4.1.2 Secondary Effectiveness Endpoint

The secondary effectiveness endpoint is the outcome of achieving $\geq 20\%$ reduction in medication-free mean diurnal IOP from baseline at 12 months. Subjects who meet any of the criteria listed in Section 4.1.1 above will be imputed as non-responders (i.e. failures) for this secondary endpoint. Similarly, the primary analyses for the secondary effectiveness endpoint will be based on the available 12-month medication-free mean diurnal IOP with the imputation described above for the subjects meet the criteria listed in Section 4.1.1. For subjects that do not meet the criteria listed in Section 4.1.1 and are discontinued prior to the 12-month visits, imputations for their missing 12-month medication-free mean diurnal IOP will be performed as the sensitivity analyses.

The proportion of subjects achieving this effectiveness endpoint (12-month IOP responder rate) will be compared between the VISCO360 group and control group. The corresponding statistical hypotheses are as follows:

$$H_0: p_v - p_c = 0 \text{ versus } H_A: p_v - p_c > 0$$

The p_v and p_c are the 12-month IOP response rates for the VISCO360 group and control group, respectively. The VISCO360 will be concluded to be superior to the control group in reducing IOP if H_0 is rejected based on one-sided significance level of 0.025.

Since the formal statistical conclusion for the secondary effectiveness endpoint will be made if and only if the null hypothesis of the primary effectiveness endpoint is rejected, no adjustment for the significance level will be performed for the secondary effectiveness endpoint.

4.2 Safety Outcomes

The safety outcomes include all intraoperative or postoperative ocular adverse events (AEs) as listed in Section VII of the study protocol, BCVA changes from baseline, results of slit lamp examination, gonioscopy findings, dilated fundus examination findings, and pachymetry.

4.3 Other Clinical Parameters

A focused questionnaire consisting of 18 questions from the CIGTS “Symptom and Health Problem Chart” (11 Visual Function items and 7 Local Eye items) will be administered. For each subject, the total score is calculated for Visual Function Symptom Impact (range from 0 to 55) and for Local Eye Symptom Impact (range from 0 to 35). No labeling claims will be made based on the PRO’s.

5.0 SEQUENCE OF PLANNED ANALYSES

5.1 Interim Analyses/FDA Annual Report Submission

No interim effectiveness analyses will be performed prior to the database closure for the endpoint analysis of 12 month IOP outcomes.

As described in Section 3.0, when the first 20 VISCO360 subjects complete the 1-month examination, an interim analysis of the safety data will be performed using all available data. Descriptive statistics (mean, median, standard deviation, minimum, and maximum for the continuous outcomes; counts and percentages for categorical variables) will be used to summarize data for each of the two study treatment groups. No postoperative IOP, non-diurnal or diurnal, will be analyzed or summarized. However, IOP associated adverse events will be reported.

Only safety data will be summarized for the FDA annual report. As will be the case for the expansion request to FDA, no postoperative IOP, non-diurnal or diurnal, will be analyzed or summarized in annual reports. Any adverse events associated with IOP would be included.

5.2 Pre-Market Submission

When all randomized subjects have either completed the 12-month follow-up examination or have discontinued from the study, the data will be analyzed based on this Statistical Analysis Plan for a premarket FDA submission.

5.3 Final Report

When all randomized subjects have either completed the 24-month or later follow-up examination or have discontinued from the study, the data will be analyzed based on this Statistical Analysis Plan.

6.0 SAMPLE SIZE CALCULATION

The sample size for the primary effectiveness endpoint and the corresponding statistical hypotheses described in Section 4.1.1 is based on the following assumptions and criteria.

- The standard deviation of change in mean diurnal IOP from baseline at 12 months is assumed to be 5.0 mmHg. Per Seymenoglu³, the mean and standard deviation (SD) of the change in IOP from baseline to 12 months was 5.5 mmHg \pm 3.8 mmHg for the pseudophakic eyes with SLT, without additional medications, without SLT retreatments, and without any glaucoma-related secondary surgical intervention. Since the study will evaluate the change in the mean diurnal IOP from baseline after washout to 12 months after washout, the SD of the endpoint is expected to be larger than the published SD of 3.8 mmHg. An SD of 5 mmHg is assumed for the study.
- Significance level is 0.025 (one-sided) and statistical power is 90% at a true mean difference of 2 mmHg.
- Two-sample *t*-test will be used.
- A yearly dropout rate of 10% is considered.
- The randomization ratio for the study is 1:1.

Based on the criteria above, the 12-month sample size for the primary effectiveness endpoint and corresponding statistical hypotheses are **133** VISCO360 and **133** control subjects at 12 months. With the yearly dropout rate of 10%, approximately **296** subjects (**148** VISCO360 and **148** controls) should be randomized.

The sample size calculation for the secondary effectiveness endpoint and the corresponding statistical hypotheses described in Section 4.1.2 is based on the following assumptions and criteria:

³ [name] and [name] (2015). Efficacy of Selective Laser Trabeculoplasty in Phakic and Pseduphakic Eyes. J. Glaucoma, 2015;24:105–110.

- The 12-month IOP response rates for the control group (p_c) is estimated are estimated to be 0.5. Per Seymennoglu, the 12-month IOP response rate was 0.62 for the pseudophakic eyes with SLT, without additional medications, without SLT retreatments, and without any glaucoma-related secondary surgical intervention. Due to the requirement of medication washout in this study, it is expected that the 12-month response rate for the control group of this study is lower than the published 0.62. Therefore, a 12-month response rate of 0.50 is assumed for the control group.
- Significance level is 0.025 (one-sided) and statistical power is 90% at a difference in the responder rate of 0.2. In other words, the power is 90% if the true p_v (the 12-month response rate of the VISCO360 group) is 0.2 and the true p_c is 0.5.
- Fisher's exact test will be used.
- A yearly dropout rate of 10% is considered.
- The randomization ratio for the study is 1:1.

Based on the criteria above, the 12-month sample size for the secondary effectiveness endpoint and corresponding statistical hypotheses are **134** VISCO360 and **134** control subjects at 12 months. With the yearly dropout rate of 10%, approximately **298** subjects (**149** VISCO360 and **149** controls) should be randomized.

Since the sample size for the secondary effectiveness endpoint is larger than that for the first effectiveness endpoint, approximately **298 randomized subjects** will be required for this study. If a 40% screening failure is considered, approximately **497** subjects should be enrolled and screened.

7.0 ANALYSIS POPULATIONS

7.1 Safety Population

The safety analysis population will contain all subjects who are randomized and for whom VISCO360 or SLT is attempted. Subjects will be grouped according to whether they undergo VISCO360 or SLT and not according to their randomization assignment (as randomized). The subjects who have aborted VISCO360 or SLT procedures will be included in the safety analysis population since the procedure has been performed or attempted.

7.2 Intent to Treat and Modified Intent to Treat Populations

The Intent to Treat (ITT) analysis population will include all subjects randomized. Subjects will be grouped according to their randomization assignment (as randomized) regardless if they actually undergo the assigned procedure. The Modified Intent to Treat (mITT) population is a subset of the ITT population. It consists of the ITT subjects that actually undergo the assigned procedure. The mITT population will be used for the primary analyses of the primary and secondary effectiveness endpoints. The ITT population will be also used for the analyses of the primary and secondary effectiveness endpoints as part of the sensitivity analyses.

7.3 Per Protocol Population

The per-protocol (PP) population is the mITT population that also meets all of the following criteria:

- Subject meets all protocol eligibility criteria.
- Subject has the 12-month examination.
- Subject does not have any major protocol deviations that are established before the data review and database closure.
- Subject that assigned to the VISCO360 study arm receive the 360-degree treatment and subjects assigned to the SLT arm receive a least a 180 degree treatment.

The PP population will be used for the analyses of the primary and secondary effectiveness endpoints as part of the sensitivity analyses.

For the analyses on the primary and secondary effectiveness endpoints based on the mITT or PP populations, the analyses will be based on the available 12-month medication-free mean diurnal IOP with the baseline-imputation for subjects who meet the criteria listed in Section 4.1.1.

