8.6 SLT PROCEDURE

The type of anesthesia will be at the surgeon's discretion.

For patients assigned to the SLT treatment arm, a single application of pilocarpine and apraclonidine (1 %) or brimonidine (0.2 % or 0.15 %) will be instilled into the operative eye prior to the laser treatment. A frequency doubled, q-switched Nd:YAG laser emitting at 532 nm with a pulse duration of 3 ns, a spot size of 400 μ m, and pulse energies ranging from 0.6 to 1.6 mJ, coupled to a slit lamp delivery system with a helium-neon laser aiming system will be used in all cases. Any mirrored gonioscopic lens that does not magnify is acceptable for use during the procedure. The laser will be focused on the trabecular meshwork using the HeNe aiming beams and a single laser pulse will be delivered at the 3 o'clock position. The laser energy will be increased or reduced by 0.1-mJ increments until fine 'champagne' bubbles are generated. During laser application, bubble formation will be monitored with each pulse to avoid excessive bubble formation and to avoid no observed response.

Additional details are included in the SLT laser manufacturer's approved instructions for performing SLT.

180° treatments of approximately 50 applications should be applied first inferiorly and then superiorly with the goal of 360° treatment. If necessary, the superior 180° SLT treatment can be performed in a separate session within 1 week of the first SLT session and the reason for deferral should be recorded. The total number of pulses delivered, the number of clock hours treated, and the total amount of energy delivered will be recorded following each treatment.

One drop of apraclonidine (1 %) or brimonidine (0.2 % or 0.15 %) should be applied immediately after the SLT procedure and an NSAID (e.g. Ketorolac 0.4%) 1 drop 4 times per day for 4 days should be prescribed following SLT.

The IOP should be checked and recorded within 1 hour of the laser procedure. An IOP increase \geq 10 mmHg should be recorded as an AE.

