8.9 FOLLOW-UP

All subjects will participate in defined follow-up visits throughout two years as follows:

- Screening (Day -45 TO -2)
- Baseline (Day -15 TO 0 after completion of medication washout)
- Surgery/SLT Procedure (Day 0)
 - If necessary, the second 180° SLT treatment can be performed in a separate session within 1 week of the first SLT session and the schedule of visits will not be altered (the Unscheduled Visit CRF will be used for this visit)
- 1 Day Postop (Day 1)
- 1 Week Postop (Day 5-9)
- 1 Month Postop (Day 21-35)
- 3 Months Postop (Day 70-98)
- 6 Months Postop (Day 150 –210)
- 12 Months Postop (Day 330 – 420)
 - At the 12 M Postoperative Visit, only subjects who are ocular hypotensive medication-free will have Diurnal IOP measurements performed. Subjects using ocular hypotensive medications at this visit will undergo medication washout and return for the 12 M Postoperative Washout Visit for Diurnal IOP measurements.
- 12 Month Washout (Day 330 – 420, after completion of medication washout)
- 18 Months Postop (Day 510 – 600)
- 24 Months Postop (Day 690 – 780)

A follow-up case report form shall be completed from source data gathered at the time the subject is examined. Unscheduled visits should also be recorded using the appropriate forms. **Table 2** provides an overview of all activities to be conducted during the clinical study.

All attempts should be made to conduct each follow-up evaluation within the specified time intervals shown in **Table 2**. Evaluations conducted outside the prescribed time period will be considered protocol deviations. Visits conducted outside scheduled timeframes will be considered an additional visit and must be documented using the Unscheduled Visit form.

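### The per-protocol set requires 360 degrees of treatment in the VISCO360 arm but only 180 degrees in the SLT arm, so this sensitivity analysis may keep half-treated controls while dropping incomplete VISCO360 cases

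*SAP*

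**What the plan says.** SAP 7.3 builds the per-protocol set from the mITT population and adds four criteria. The last concerns extent of treatment: VISCO360 subjects must "receive the 360-degree treatment and subjects assigned to the SLT arm receive a least a 180 degree treatment". The same section gives the set its role: "The PP population will be used for the analyses of the primary and secondary effectiveness endpoints as part of the sensitivity analyses".

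Protocol 8.6 describes the control procedure: "180° treatments of approximately 50 applications should be applied first inferiorly and then superiorly with the goal of 360° treatment". The flexibility it offers is in timing: if necessary, "the superior 180° SLT treatment can be performed in a separate session within 1 week of the first SLT session", with the reason for deferral recorded. Protocol 8.9 repeats the one-week allowance and leaves the visit schedule unchanged. Section 8.6 also requires that "the number of clock hours treated, and the total amount of energy delivered will be recorded following each treatment".

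The primary analysis uses a different set. SAP 7.2 states: "The mITT population will be used for the primary analyses of the primary and secondary effectiveness endpoints". That population is defined by having undergone the assigned procedure, with no criterion on degrees treated.

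**The concern.** A per-protocol analysis is meant to show the treatment contrast when both procedures are delivered as planned. Here the extent filter is strict in one arm and loose in the other. A VISCO360 eye that falls short of 360 degrees leaves the set. An SLT eye whose second half never takes place stays in, at half the extent that Protocol 8.6 aims for. No visible text explains the difference.

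The claim under test is superiority of VISCO360 on IOP reduction. If less extensive treatment lowers IOP less, which is the natural reason for having an extent criterion at all, the rule works in favour of the investigational arm. The trial is single-masked and the operator knows the assignment, so the extent of SLT is decided by someone who is not blind to it. This is a further reason for an even-handed completeness rule. At stake is whether a per-protocol result that agrees with the primary analysis can be read as neutral support.

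**Working it through.** **The plan's own figures, for context.** SAP 6.0 gives SD 5 mmHg, difference 2 mmHg, one-sided 0.025 and 90% power. The normal approximation gives n = 2 × (1.960 + 1.282)² × 5² / 2² = 131.4, so 132 per arm; the t-based solution is 132.3, so 133, as stated. With 10% dropout, 133 / 0.90 = 147.8, so 148. The final total of 298 comes from the secondary endpoint: 134 / 0.90 = 148.9, so 149 per arm. None of this uses the per-protocol set, and no stated number is wrong on this point.

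**The rules side by side.**

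| | VISCO360 | SLT |
|---|---|---|
| Extent intended | procedure steps blacked out in Protocol 8.5; 360 degrees read from SAP 7.3 | goal of 360 degrees, second half within 1 week (Protocol 8.6) |
| Extent needed for per-protocol | 360 degrees | at least 180 degrees |
| Short of 360 degrees | excluded | kept, if 180 degrees or more |
| Extent needed for mITT or ITT | none | none |

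**Size of a possible tilt.** Let f be the share of per-protocol SLT eyes treated over 180 degrees only, and s the shortfall in their IOP reduction against full SLT. The per-protocol SLT mean reduction is then understated by f × s. Neither quantity is in the documents, so both are assumed.

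- f = 5%, s = 1 mmHg: 0.05 × 1 = 0.05 mmHg, which is 2.5% of the 2 mmHg design difference.
- f = 20%, s = 2 mmHg: 0.20 × 2 = 0.40 mmHg, which is 20% of it.

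As a second route, take s as a fraction r of the 5.5 mmHg mean SLT reduction cited in SAP 6.0, with r = 0.25 to 0.5 (also assumed). The tilt is b = f × r × 5.5. With SE = 5 × √(2/133) = 0.613 mmHg, the chance of a one-sided 0.025 rejection when VISCO360 truly equals full SLT is Φ(b / 0.613 − 1.96):

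| f | b (mmHg) | chance of rejection |
|---|---|---|
| 0 | 0 | 2.5% |
| 5% | 0.07 to 0.14 | 3.2% to 4.1% |
| 10% | 0.14 to 0.28 | 4.1% to 6.5% |
| 20% | 0.28 to 0.55 | 6.5% to 14.4% |

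The 133 per arm is the planned 12-month number. The per-protocol set would be smaller, so these percentages are approximate.

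**What is not added.** Removing incomplete VISCO360 eyes moves the per-protocol estimate away from the mITT estimate, but it does not bias it against a comparison of two fully delivered procedures. That bias comes from the SLT side, and only f × s is counted.

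**The case against.** A reader might infer that the per-protocol analysis sets complete VISCO360 against partly delivered SLT. The documents do not support that. The SLT threshold is a minimum, so it admits every full 360-degree SLT treatment. Protocol 8.6 steers sites toward 360 degrees, and no expected share of 180-degree eyes is given. The set can include such eyes, and the text goes no further.

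It can also be said that 360 degrees is worded as a goal for SLT, so an eye treated over 180 degrees is not clearly a deviation and may belong in a per-protocol set. Exclusion criterion 16 in the protocol synopsis accepts either one prior 180-degree or one prior 360-degree SLT application as history. This has some weight, but criterion 16 describes past treatment, not this trial's control, and the SAP does not offer it as a reason for unequal thresholds.

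Part of the record cannot be seen. The VISCO360 procedure steps are blacked out, and SAP 9.4.3, to which the SAP refers for the missing-data sensitivity analyses, is not visible. An analysis by extent of treatment could exist there. The exclusion for major protocol deviations might remove some half-treated SLT eyes, but the visible text lists no such deviations, and an explicit 180-degree threshold suggests these eyes are meant to stay.

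Finally, the size rests on assumed inputs, and the consequence is confined to one sensitivity analysis. Both statements are correct. They limit the weight of the point, but the unequal rule remains in the text.

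**Conclusion.** The point holds in a limited form. SAP 7.3 applies unequal completeness rules, and the per-protocol analysis of both effectiveness endpoints may keep half-treated SLT eyes while dropping incomplete VISCO360 eyes.

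Two stronger readings are tempting. One is that the rule can only favour VISCO360. That depends on incomplete treatment lowering IOP less, which is plausible but not shown by any outcome data by extent in the documents. The other is that the superiority conclusion is compromised. It is not: the formal tests use the mITT population, the ITT sensitivity analysis also has no extent criterion, and the sample size does not depend on the per-protocol set.

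Under the assumption on direction, the tilt is about 0.05 to 0.40 mmHg for 5% to 20% of SLT eyes at 180 degrees and a 1 to 2 mmHg shortfall. This is below the planned standard error of 0.61 mmHg. It is large enough to weaken the per-protocol analysis as a neutral check, and cheap to remove. The point should be fixed, but it does not threaten the primary result.

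**What to change.** Before database lock, which is when SAP 1.0 allows amendments, reconcile SAP 7.3 with Protocol 8.6 and define per-protocol completeness by one standard in both arms: the full extent that the protocol intends for the assigned procedure. For SLT, this can be derived from the clock hours already recorded under Protocol 8.6, counting a second session held within the permitted week. If the sponsor keeps the 180-degree threshold, the SAP should state the reason and also report the per-protocol analysis under the symmetric rule.

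The cost is one sentence in SAP 7.3 and no new SLT data. The SLT per-protocol group may become slightly smaller, and the stricter rule is a further post-randomization exclusion, so the number of eyes removed for extent should be shown by arm. The change concerns the analysis set only; it does not say which extent of treatment is clinically right.

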8.0 DATA HANDLING

8.1 General Procedure for Data Summary

Descriptive statistics on continuous variables will include mean, standard deviation, median, minimum, and maximum. Confidence intervals for change from baseline will be included for selected endpoints. Categorical variables will be summarized using frequency counts and percentages. Exact confidence intervals for point estimates may be provided. Statistical testing will be one-sided with a significance level of 0.025 or two-sided significance level of 0.05) unless specify otherwise. Data listings of individual subject data may be provided.

8.2 Definition

8.2.1 Baseline

The baseline values are those that are obtained at the closest visit prior to the surgery. The arithmetic difference between the baseline and a post-baseline (post-operative for this study) are as follows:

Change from baseline = (post-baseline value – baseline value)

Percent change from baseline = Change from baseline ÷ baseline value × 100.

8.2.2 Mean Diurnal IOP

In order to determine the mean diurnal intraocular pressure (IOP) measurements, IOP will be taken at 9:00AM \pm 1.5 hours, 12:00PM \pm 1 hour, and 4:00PM \pm 2 hours. Each time IOP is measured, two measurements should be taken and the mean recorded on the case report form unless they differ by more than 2mmHg in which case a third measurement is taken and the median value is recorded. The three IOP measurements should then be averaged to determine the mean diurnal IOP.

8.2.3 Day 0 and Study Day

The Day 0 is the surgery day. The study day is defined as the study date – date of surgery. A positive study day is for a post-surgery date; a negative study day is for a pre-surgery date.

8.2.4 Visit Windows

Visit	Window
Screening	Day -45 to -2
Baseline	Day -15 to -1, after completion of medication washout
Surgery/SLT Procedure	Day 0 (up to -72 hours)
1 Day Postop	Day 1
1 Week Postop	Day 5-9
1 Month Postop	Day 21-35
3 Months Postop	Day 70-98
6 Months Postop	Day 150 –210
12 Months Postop	Day 330 – 420
12 Month Washout	Day 330 – 420, after completion of medication washout
18 Months Postop	Day 510 – 600
24 Months Postop	Day 690 – 780

8.2.5 Washout

For subjects taking hypotensive medications at screening and 12 months after surgery, the minimum wash-out periods are specified in the study protocol.

8.2.6 Age Calculation

Age will be calculated for each subject by $(\text{Date of Surgery} - \text{Date of Birth} + 1) \div 365.25$ and rounded down to the nearest integer. For subjects enrolled but not undergoing surgery, the age will be calculated by $(\text{Date of Screening} - \text{Date of Birth} + 1) \div 365.25$ and rounded down to the nearest integer, if necessary.

